**Missing outcome data**

Missing efficacy data and partial dates related to clinical outcomes will not be imputed.

---

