#### 4.1.2 EXPANSION COHORT DESIGN

Participants with tumors demonstrating PK-response in Phase 0 will continue treatment with the same dose continuously for 21 days in 28d cycles after surgery. This will constitute the Expansion Cohort component of the study. PD biomarkers will be included for exploratory analyses. Expansion Cohort participants will be contacted every 3 months by letter or phone for collection of survival data.

Participants will be treated until unacceptable toxicity is observed, or until disease progression as assessed by RANO criteria.

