### 9.4 STATISTICAL ANALYSES

#### 9.4.1 ANALYSIS OF THE PRIMARY EFFICACY ENDPOINT(S)

Phase 0 endpoint PK Analysis:

A positive PK response will be unbound concentrations of infigratinib (along with its active metabolites) reaching 5-fold higher than their respective cell-free biochemical IC50 values within the non-enhancing region of the tumor.

Expansion cohort endpoint: For the primary endpoint of PFS rate at 6 months:

- Progression-free survival (PFS) is defined as the number of days from the date of surgery to the first documentation of progression or death due to any cause. Participants who remain alive without progression will be censored for PFS at the date of their last tumor assessment.

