## A Phase 0 Study of Infigratinib in Recurrent Glioblastoma Patients Protocol 2020-08

Participants removed from study treatment due to symptomatic deterioration will be considered as having progression for the purposes of the primary endpoint.

- Disease progression is defined per RANO criteria for high-grade glioma patients.

---

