#### **Computation of Duration**

Duration for time variables based on two dates, e.g., Start Date and End Date, will be calculated as (End Date – Start Date + 1) (in days) unless otherwise specified.

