#### 9.4.6 EXPLORATORY ANALYSES

Systemic plasma PK profile parameters ( $T_{max}$ ,  $C_{max}$ ,  $t_{1/2}$ ,  $AUC_{0-24h}$ ) for total and unbound levels will be determined for infigratinib. Plasma pharmacokinetic parameters of total and unbound drugs will be estimated from individual plasma concentration–time profiles using the noncompartmental analysis with Phoenix WinNonlin software (Certara USA, Inc.). Kinetic parameters, including the maximum plasma concentration ( $C_{max}$ ), time to reach  $C_{max}$  ( $T_{max}$ ), area under the curve during one dosing interval ( $AUC_{\tau}$ ), drug elimination half-life ( $t_{1/2}$ ), will be calculated by modeling group mean data at each time point.

Overall Survival: the distributions of survival outcomes (OS) will be summarized using Kaplan-Meier Curves, and their median times and associated 95% confidence intervals will be estimated using Kaplan-Meier estimates. Overall survival is defined as the number of days from the date of surgery to the date of death due to any cause. Participants alive at the time of analysis will be censored at the date of last contact.

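### Section 9.4.5 bars completing partial outcome dates, so a known death or progression with an incomplete date has no usable time in the OS or PFS analysis

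*Combined protocol and SAP*

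**What the plan says.** The rule is in Section 9.4.5, under Missing outcome data: "Missing efficacy data and partial dates related to clinical outcomes will not be imputed". The same section says that a duration between two dates "will be calculated as (End Date – Start Date + 1) (in days) unless otherwise specified".

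Section 9.4.1 introduces the expansion endpoint with "For the primary endpoint of PFS rate at 6 months" and defines PFS as "the number of days from the date of surgery to the first documentation of progression or death due to any cause". On censoring it says: "Participants who remain alive without progression will be censored for PFS at the date of their last tumor assessment". It adds: "Participants removed from study treatment due to symptomatic deterioration will be considered as having progression for the purposes of the primary endpoint". No estimator is named for the six-month rate.

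Section 9.4.6 says: "Overall survival is defined as the number of days from the date of surgery to the date of death due to any cause". OS is summarised by Kaplan-Meier, and those still living are censored at last contact.

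On data collection, Section 4.1.2 says: "Expansion Cohort participants will be contacted every 3 months by letter or phone for collection of survival data". The End of Study Definition extends survival follow-up to as much as 5 years after the last dose. Section 9.1 states that there will be no separate SAP, so Section 9 is where a rule for these cases would have to be.

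**The concern.** The plan foresees partial outcome dates and forbids completing them, but does not say what then happens to the event. A death reported by letter or phone up to three months later may come with only a month, or only a year. The participant is known to have died, so the event itself is not missing; only part of its date is. If the rule makes the analyst discard or censor that event, information the trial holds is lost from a cohort of about 10, and each analyst may resolve it differently after seeing the data.

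**Working it through.** **Can the event be timed?** PFS and OS are numbers of days, and the duration formula subtracts one date from another. Both need a complete end date. With a partial date and no imputation, neither can be computed.

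**Does a censoring rule catch it?** The PFS rule covers people alive without progression. The OS rule covers people still living. Someone known to have died fits neither, and someone known to have progressed does not fit the PFS rule. In an analysis in days, what remains is to drop the participant, to censor a known event, or to breach Section 9.4.5.

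**Cohort size (Section 9.2).** 400 operations per year × 5% × 50% capture × 2 years = 20, which reproduces the stated Phase 0 number. Half are expected to expand: 20 × 0.50 = 10.

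**When is PFS6 affected?** Six months is 6 × 30.4375 = 182.6 days under Section 9.4.5. A partial date leaves six-month status open only if its earliest and latest possible dates fall on opposite sides of that day. This was simulated with events uniform over the first year after surgery and surgery dates spread over two years, both assumptions:

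- Day missing: status undetermined in 8.05% of cases. Hand check: 30.4375 / 365 = 8.3%.
- Day and month missing: 74.9%. Here the only bounds were the surgery date and the ends of the calendar year. Bounds from the last contact and the notification date would narrow the interval.

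**Effect of one lost early event on PFS6, n = 10.** The documents give no PFS6 rate, so 20% to 40% is assumed.

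| Truly progression-free | All events kept | One early event dropped | Counted event-free |
|---|---|---|---|
| 2 | 2/10 = 20% | 2/9 = 22.2% | 3/10 = 30% |
| 3 | 3/10 = 30% | 3/9 = 33.3% | 4/10 = 40% |
| 4 | 4/10 = 40% | 4/9 = 44.4% | 5/10 = 50% |

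Dropping adds 2.2, 3.3 or 4.4 points; counting as event-free adds 10. In the 30% case, a Kaplan-Meier estimate with assumed event days 35, 60, 75, 90, 110, 135, 160, 200, 230 and 260, and one of the first seven censored about 45 days early, gives 33.3% to 37.5% instead of 30%.

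**Direction for OS.** Censoring a known death pushes the curve up from the time of that death onward. Dropping a death can go either way. With deaths at months 1 to 10 the Kaplan-Meier median is 5. Dropping those at months 8, 9 and 10 leaves seven deaths; survival is 4/7 = 57% after month 3 and 3/7 = 43% after month 4, so the median falls to 4.

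**The case against.** The strongest reply is that the rule says only that dates are not completed; it does not say that events are excluded. A reader might infer that an event with a partial date can never count towards PFS6. The documents do not support that. PFS6 is a status at a fixed time with no estimator named, and a month-only date settles that status in about 92% of cases under the assumption above. Progression runs to its first documentation, normally a dated scan or visit, and symptomatic deterioration counts as progression by status.

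A reader might also infer that the rule inflates both PFS6 and median OS. For OS that is not general, as the last example shows.

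Three further points limit the practical weight. Section 10.1.8 sends missing data back to sites for resolution, so only dates that survive queries are affected. Letter and phone follow-up starts after the 30-day safety call, by which time many participants will already have a documented progression date, so this route feeds mainly OS, which is exploratory. And Section 9.1 makes the analyses descriptive.

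All of this stands, and it narrows the point without removing it. Death from any cause is a PFS event, so the gap is not confined to OS. For Kaplan-Meier OS, any incomplete death date that survives querying leaves no usable time. The absence of a stated exclusion does not help, because the plan bars the usual remedy and offers no other.

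**Conclusion.** The point holds in a limited form. Section 9.4.5 bars completing partial outcome dates while the definitions of OS and PFS require complete ones, and no censoring rule covers a known event. The main exposure is OS; PFS6 is touched only when the possible dates straddle day 182.6.

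The size is conditional. If one early event is lost in a cohort of about 10, PFS6 rises by 2 to 4 points (dropped) or 10 points (counted event-free), at an assumed true rate of 20% to 40%. The documents do not say how many dates will stay incomplete, and no expected number is claimed here. That relatives may supply only a month or a year is a reasonable inference from remote follow-up, not a statement in the plan. No test or decision rule depends on the result, so the case for change rests on keeping known events and settling their handling in advance.

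**What to change.** Amend the missing-outcome paragraph of Section 9.4.5 as follows:

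- A known death or progression is always kept as an event.
- For PFS6, if the earliest and latest possible dates fall on the same side of six months, classify the participant by those bounds.
- Otherwise, and wherever a time in days is needed, use a prespecified date: a missing day becomes the 15th, and a missing month becomes the midpoint of the possible interval. The date may not precede the last date known alive (for progression, known progression-free) or follow the notification date.
- Repeat the analysis at the earliest and at the latest possible date.
- Leave missing response values unimputed, as now.

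The 15th is one convention among several; what matters is that it is fixed beforehand and bounded. The cost is a few sentences. The downside is about two weeks of date uncertainty when only the day is missing, and more when the month is missing too. In that second case the convention may itself decide six-month status, and the two sensitivity analyses would show it.

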#### 9.4.6 EXPLORATORY ANALYSES

Systemic plasma PK profile parameters ( $T_{max}$ ,  $C_{max}$ ,  $t_{1/2}$ ,  $AUC_{0-24h}$ ) for total and unbound levels will be determined for infigratinib. Plasma pharmacokinetic parameters of total and unbound drugs will be estimated from individual plasma concentration–time profiles using the noncompartmental analysis with Phoenix WinNonlin software (Certara USA, Inc.). Kinetic parameters, including the maximum plasma concentration ( $C_{max}$ ), time to reach  $C_{max}$  ( $T_{max}$ ), area under the curve during one dosing interval ( $AUC_{\tau}$ ), drug elimination half-life ( $t_{1/2}$ ), will be calculated by modeling group mean data at each time point.

Overall Survival: the distributions of survival outcomes (OS) will be summarized using Kaplan-Meier Curves, and their median times and associated 95% confidence intervals will be estimated using Kaplan-Meier estimates. Overall survival is defined as the number of days from the date of surgery to the date of death due to any cause. Participants alive at the time of analysis will be censored at the date of last contact.

## 10 SUPPORTING DOCUMENTATION AND OPERATIONAL CONSIDERATIONS

### 10.1 REGULATORY, ETHICAL, AND STUDY OVERSIGHT CONSIDERATIONS

#### 10.1.1 INFORMED CONSENT PROCESS

In obtaining and documenting informed consent, the investigator must comply with applicable regulatory requirements (e.g., 45 CFR Part 46, 21 CFR Part 50, 21 CFR Part 56) and should adhere to ICH GCP. Prior to the beginning of the trial, the investigator should have the IRB's written approval for the protocol and the written informed consent form(s) and any other written information to be provided to the participants.

##### 10.1.1.1 CONSENT AND OTHER INFORMATIONAL DOCUMENTS PROVIDED TO PARTICIPANTS

Consent forms describing in detail the study intervention, study procedures, and risks are given to the participant and written documentation of informed consent is required prior to starting intervention/administering study intervention.

##### 10.1.1.2 CONSENT PROCEDURES AND DOCUMENTATION

Informed consent is a process that is initiated prior to the individual's agreeing to participate in the study and continues throughout the individual's study participation. Consent forms will be Institutional Review Board (IRB)-approved and the participant will be asked to read and review the document. The investigator will explain the research study to the participant and answer any questions that may arise. A verbal explanation will be provided in terms suited to the participant's comprehension of the purposes, procedures, and potential risks of the study and of their rights as research participants. Participants will have the opportunity to carefully review the written consent form and ask questions prior to signing. The participants should have the opportunity to discuss the study with their family or surrogates or think about it prior to agreeing to participate. The participant will sign the informed consent document prior to any procedures being done specifically for the study. Participants must be informed that participation is voluntary and that they may withdraw from the study at any time, without prejudice. A copy of the informed consent document will be given to the participants for their records. The informed consent process will be conducted and documented in the source document (including the date), and the form signed, before the participant undergoes any study-specific procedures. The rights and welfare of the participants will be protected by emphasizing to them that the quality of their medical care will not be adversely affected if they decline to participate in this study.

#### 10.1.2 STUDY DISCONTINUATION AND CLOSURE

This study may be temporarily suspended or prematurely terminated if there is sufficient reasonable cause. Written notification, documenting the reason for study suspension or termination, will be provided by the suspending or terminating party to study participants, investigator(s), funding agency, the Investigational New Drug (IND) sponsor and regulatory authorities. If the study is prematurely terminated or suspended, the Principal Investigator (PI) will promptly inform study participants, the Institutional Review Board (IRB), and will provide the reason(s) for the termination or suspension. Study participants will be contacted, as applicable, and be informed of changes to study visit schedule.

Circumstances that may warrant termination or suspension include, but are not limited to:

A Phase 0 Study of Infigratinib in Recurrent Glioblastoma Patients  
Protocol 2020-08

- Determination of unexpected, significant, or unacceptable risk to participants
- Demonstration of efficacy that would warrant stopping
- Insufficient compliance to protocol requirements
- Data that are not sufficiently complete and/or evaluable
- Determination that the primary endpoint has been met
- Determination of futility

Study may resume once concerns about safety, protocol compliance, and data quality are addressed, and satisfy the IND sponsor, IRB and/or Food and Drug Administration (FDA).

---

#### 10.1.3 CONFIDENTIALITY AND PRIVACY

Participant confidentiality and privacy is strictly held in trust by the participating investigators, their staff, and the sponsor(s) and their interventions. This confidentiality is extended to cover testing of biological samples and genetic tests in addition to the clinical information relating to participants. Therefore, the study protocol, documentation, data, and all other information generated will be held in strict confidence. No information concerning the study or the data will be released to any unauthorized third party without prior written approval of the sponsor.

All research activities will be conducted in as private a setting as possible.

The study monitor, other authorized representatives of the sponsor, representatives of the Institutional Review Board (IRB), regulatory agencies or pharmaceutical company supplying study product may inspect all documents and records required to be maintained by the investigator, including but not limited to, medical records (office, clinic, or hospital) and pharmacy records for the participants in this study. The clinical study site will permit access to such records.

The study participant's contact information will be securely stored at each clinical site for internal use during the study. At the end of the study, all records will continue to be kept in a secure location for as long a period as dictated by the reviewing IRB, Institutional policies, or sponsor requirements.

Study participant research data, which is for purposes of statistical analysis and scientific reporting, will be transmitted to and stored at the IBTC-CC. This will not include the participant's contact or identifying information. Rather, individual participants and their research data will be identified by a unique study identification number. The study data entry and study management systems used by clinical sites and by IBTC-CC research staff will be secured and password protected. At the end of the study, all study databases will be de-identified and archived at the IBTC-CC.

---

#### 10.1.4 FUTURE USE OF STORED SPECIMENS AND DATA

Data collected for this study will be analyzed and stored at the IBTC-CC. After the study is completed, the archived data will be transmitted to and stored at the Data Repository, for use by other researchers including those outside of the study. Permission to transmit data to the Data Repository will be included in the informed consent.

With the participant's approval and as approved by local Institutional Review Boards (IRBs), de-identified biological samples will be stored at the Ivy Brain Tumor Center Laboratory with the same goal as the sharing of data with the Data Repository. These samples could be used to research the causes of brain tumors, its complications and other conditions for which individuals with brain tumors are at increased risk, and to improve treatment. The Data Repository will also be provided with a code-link that will allow

A Phase 0 Study of Infigratinib in Recurrent Glioblastoma Patients  
Protocol 2020-08

linking the biological specimens with the phenotypic data from each participant, maintaining the blinding of the identity of the participant.

[figure not shown]
During the conduct of the study, an individual participant can choose to withdraw consent to have biological specimens stored for future research. However, withdrawal of consent with regard to biosample storage may not be possible after the study is completed.

When the study is completed, access to study data and/or samples will be provided through the IBTC.

---

#### 10.1.5 KEY ROLES AND STUDY GOVERNANCE

The following committees will carry out the research planning and implementation of IBTC.

The Scientific Review Committee (SRC) is a group of experts who assess the scientific merit and feasibility of drug compounds to be developed into clinical trial protocols. The SRC will review the scientific merit, participant availability and review of progress including study objectives and participant accrual.

The IBTC Coordinating Center (IBTC-CC) is a coordinating committee as defined by GCP E6 1.18. The Sponsor-Investigator may delegate responsibilities to the IBTC-CC. At the beginning of each trial, the IBTC-CC will outline the transferred obligation from the Sponsor-Investigator to the IBTC-CC under 21 CFR 312.

The DSMB will act in an advisory capacity to monitor participant safety, evaluate the progress of the study, to review procedures for maintaining the confidentiality of data, the quality of data collection, management, and analyses.

---

#### 10.1.6 SAFETY OVERSIGHT

Safety oversight will be under the direction of a Data and Safety Monitoring Board (DSMB) composed of individuals with the appropriate expertise, which may include neurosurgery, neuroradiology, biostatistics, and oncology. Members of the DSMB should be independent from the study conduct and free of conflict of interest, or measures should be in place to minimize perceived conflict of interest. The DSMB will meet at least semiannually to assess safety and efficacy data on each arm of the study. The DSMB will operate under the rules of an approved charter that will be written and reviewed at the organizational meeting of the DSMB. At this time, each data element that the DSMB needs to assess will be clearly defined. The

A Phase 0 Study of Infigratinib in Recurrent Glioblastoma Patients  
Protocol 2020-08

DSMB will provide its input to the IBTC Coordinating Center and the Sponsor-Investigator and reported to the IRBs as applicable.

---

#### 10.1.7 CLINICAL MONITORING

Clinical site monitoring is conducted to ensure that the rights and well-being of trial participants are protected, that the reported trial data are accurate, complete, and verifiable, and that the conduct of the trial is in compliance with the currently approved protocol/amendment(s), with International Conference on Harmonisation Good Clinical Practice (ICH GCP), and with applicable regulatory requirement(s).

- Monitoring for this study will be performed by IBTC Coordinating Center.
- Details of clinical site monitoring are documented in a Data and Safety Monitoring Plan (DSMP). The DSMP describes in detail who will conduct the monitoring, at what frequency monitoring will be done, at what level of detail monitoring will be performed, and the distribution of monitoring reports.

---

#### 10.1.8 QUALITY ASSURANCE AND QUALITY CONTROL

Each clinical site will perform internal quality management of study conduct, data and biological specimen collection, documentation and completion.

Quality control (QC) procedures will be implemented beginning with the data entry system and data QC checks that will be run on the database will be generated. Any missing data or data anomalies will be communicated to the site(s) for clarification/resolution.

Following the Data and Safety Monitoring Plan, the monitors will verify that the clinical trial is conducted and data are generated and biological specimens are collected, documented (recorded), and reported in compliance with the protocol, International Conference on Harmonisation Good Clinical Practice (ICH GCP), and applicable regulatory requirements.

The investigational site will provide direct access to all trial related sites, source data/documents, and reports for the purpose of monitoring and auditing by the sponsor, and inspection by local and regulatory authorities.

---

